26.7 Rationale for prohibited concomitant drugs and therapies

- (1) The use of those drugs is considered inappropriate to evaluate the efficacy of the study drugs.
- (2) Safety information is not available for drug-drug interactions between the study treatment and other study drugs. This criterion has been established to ensure the safety of subjects.
- (3) Those drugs may enhance the side effect of TAS-118 and S-1.
- (4) Those drugs may enhance the side effect of TAS-118 and S-1.
- (5) The use of those therapies is considered inappropriate to evaluate the efficacy of the study drugs.

26.8 Rationale for precautions for concomitant drugs and therapies

- (1) Tegafur may enhance the effect of warfarin potassium.
- (2) Tegafur may inhibit the metabolism of phenytoin to increase the blood phenytoin concentration, so that phenytoin toxicities may occur (such as queasy/vomiting, nystagmus, and movement disorder).
- (3) Concomitant administration of these drugs with CDDP may enhance renal disorder and ototoxicity.
- (4) Concomitant administration of the drug with CDDP may enhance renal disorder.
- (5) Concomitant administration of the drug with CDDP may enhance ototoxicity.

[figure not shown]

Appendix 1. Definition of EGJ

The area extending 2 cm above to 2 cm below the esophagogastric junction (EGJ) is designated the EGJ area. Tumors having their epicenter in this area are designated EGJ carcinomas irrespective of histological type.

Appendix 2. Definition of HER2 status¹¹

HER2 status	Criteria
Positive (Meet either criteria)	1. Score as 3+ on immunohistochemistry (IHC) 2. Score as 2+ on IHC and Positive on fluorescence in situ hybridization (FISH)
Negative	Other

Using Silver *in situ* hybridization (SISH) or other tests instead of FISH test for confirmation of HER2 status are allowed.

Appendix 3. Cockcroft-Gault formula

The Cockcroft-Gault formula:

$$\text{Estimated creatinine clearance (mL/min)} = (140 - \text{age}) \times \text{Body weight (kg)} / [(72 \times \text{Serum creatinine (mg/dL)})]$$

For women, the obtained value is multiplied by a factor of 0.85.

Appendix 4. Du Bois formula

The BSA will be calculated by the IWRS using the following DuBois formula. All BSA calculations are rounded down, so the number must be set to 2 decimal places.

$$\text{BSA (m}^2\text{)} = ([\text{Body Weight (kg)}]^{0.425} \times [\text{Height (cm)}]^{0.725}) \times 0.007184$$

Appendix 5. ECOG Performance status (PS)

GRADE	ECOG
0	Fully active, able to carry on all pre-disease performance without restriction
1	Restricted in physically strenuous activity but ambulatory and able to carry out work of a light or sedentary nature, eg, light house work, office work
2	Ambulatory and capable of all self-care but unable to carry out any work activities. Up and about more than 50% of waking hours
3	Capable of only limited self-care, confined to bed or chair more than 50% of waking hours
4	Completely disabled. Cannot carry on any self-care. Totally confined to bed or chair
5	Dead

From: Oken MM, Creech, RH, Tormey DC, et al. Toxicity and response criteria of the Eastern Cooperative Oncology Group. *Am J Clin Oncol* 1982;5:649-55.

ECOG	Eastern Cooperative Oncology Group
FAS	Full analysis set
HR	Hazard ratio
IDMC	Independent data monitoring committee
IWRS	Interactive web response system
L-OHP	(SP-4-2)-[(1 R , 2 R)-Cyclohexane-1, 2-diamine- κ N, κ N'] [ethanedioato(2-)- κ O ¹ , κ O ²]platinum: oxaliplatin (JAN)
MedDRA	Medical Dictionary for Regulatory Activities
MST	Median survival time
NE	Not evaluable (response associated with antitumor activity)
ORR	Overall response rate
OS	Overall survival
PD	Progressive disease (response associated with antitumor activity)
PFS	Progression-free survival
PR	Partial response
PS	Performance status
RECIST	Response evaluation criteria in solid tumors ¹⁾
RMST	Restricted mean survival time
SD	Stable disease (response associated with antitumor activity)
SOC	System organ class
TTF	Time to treatment failure

1. Scope and Objective

1.1. Positioning of Statistical Analysis Plan

This statistical analysis plan provides the details of the statistical analyses to be conducted in the primary and final evaluations in “An open-label randomized multi-center phase III study of TAS-118 plus Oxaliplatin versus S-1 plus Cisplatin as first-line therapy in patients with advanced gastric cancer” [REDACTED].

1.2. Study Objective

To compare the following endpoints for TAS-118/oxaliplatin (L-OHP) (study arm) with S-1/cisplatin (CDDP) (control arm) in patients with advanced gastric cancer:

Primary

- Overall survival (OS)

Secondary

- Progression-free survival (PFS)
- Time to treatment failure (TTF)
- Overall response rate (ORR)
- Disease control rate (DCR)
- Safety

1.3. Changes from Protocol

The full analysis set (FAS) is defined as “patients in as-treated (AT) population who have gastric cancer at randomization” in the protocol version 3.0, but the definition is changed to “patients in AT population who have advanced gastric cancer at randomization” in this statistical analysis plan. Since this study involves patients with advanced gastric cancer as specified in the primary objective, the protocol has not been revised, and the detailed definition of FAS is specified in the statistical analysis plan as determined in the discussion with medical advisor and the statistical advisor.

2. Main Statistical Considerations in the Study Design and Planned Sample Size

2.1. Planned Sample Size

2.1.1. Planned Sample Size

Target number of patients at study initiation: 686 subjects (TAS-118/L-OHP arm: 343 subjects, S-1/CDDP arm: 343 subjects); target number of patients included in the FAS: 650 subjects (TAS-118/L-OHP arm: 325 subjects, S-1/CDDP arm: 325 subjects)

2.1.2. Rationale for Sample Size Determination Before Study Initiation

In a randomized phase II study of S-1/leucovorin (LV) therapy, S-1/LV/L-OHP (SOL) therapy, and S-1/CDDP therapy in patients with unresectable, advanced/recurrent gastric cancer ([REDACTED] [REDACTED]) the median survival time (MST) was 12.6 months in the S-1/CDDP arm and 18.4 months in the SOL arm. In the SOS trial, which was conducted in Japan and Korea,⁴⁾ the MST was 13.9 months in the S-1/CDDP (5-week interval) arm (15.5 months in Japanese subjects). Taking into account the ratio of the sample size between Japan and Korea and the target population in the present study, the MST is assumed to be 14.5 months in the S-1/CDDP arm and 19.33 months in the TAS-118/L-OHP arm (hazard ratio of TAS-118/L-OHP versus S-1/CDDP, 0.75).

With an overall significance level of 5% (two-sided) in the entire study, the Lan and DeMets alpha spending function (O'Brien-Fleming type)⁵⁾ was used to split the significance level for one benefit

evaluation in an interim analysis. Assuming that test statistics in the interim analysis and the primary analysis for the primary evaluation would follow a bivariate normal distribution, the boundaries $z_{\alpha 1}$ and $z_{\alpha 2}$ that meet the formula below are 2.9627 and 1.9687, respectively, and the corresponding nominal significance levels are 0.305% and 4.899% (two-sided), respectively, in the interim analysis and the primary analysis for the primary evaluation. The information fraction is assumed to be 0.5 because the interim analysis will be conducted when half the specified number of events have been observed.

$$P(Z_1 \geq z_{\alpha 1}) = 2 \times \left\{ 1 - \Phi \left(\frac{Z_{1-\frac{\alpha}{2}}}{\sqrt{t}} \right) \right\} = 0.001525$$

$$P(Z_1 \geq z_{\alpha 1}, Z_2 \geq z_{\alpha 2}) = 0.025$$

$\alpha 1$: one- sided significance level in an interim analysis,

$\alpha 2$: one- sided significance level in the primary analysis for the primary evaluation,

t : information fraction, α : overall one- sided significance level

On the condition that the survival time is exponentially distributed in both arms, with a two-sided significance level of 4.899% as calculated above and 85% power, 437 events will be required to test whether TAS-118/L-OHP is superior to S-1/CDDP with respect to survival time in the primary evaluation, as calculated using the Schoenfeld method below:⁶⁾

$$\text{Required number of events} = \frac{\left(Z_{1-\frac{\alpha}{2}} + Z_{1-\beta} \right)^2}{r_1 \times r_2 \times (\log(\Lambda))^2}$$

α : two- sided significance level, $1-\beta$: power, Λ : hazard ratio,

r_1 : randomization ratio in Arm A, r_2 : randomization ration in Arm B

Assuming that patients would be uniformly accumulated for an accrual period of 17 months and be followed up for 19 months, the target sample size is estimated to be 650 patients according to the formula below.⁷⁾ In this case, approximately 38 patients need to be enrolled per month; however, the accrual period is set at 19 months because accrual may be slower than required and approximately 5% of patients may be additionally excluded from the FAS, and therefore, the total sample size is calculated to be 686 patients in the overall two groups.

$$\text{Target sample size} = \text{Required number of events} / \sum_i r_i \left(1 - \frac{e^{-\lambda_i Y} (1 - e^{-\lambda_i X})}{\lambda_i X} \right)$$

i : arm, r_i : randomization ratio in Arm i , λ_i : hazard in Arm i ,

X : accrual period, Y : follow-up period

Subjects can be additionally enrolled when death events occur less frequently than expected. If the number of subjects to be enrolled is increased above 686 subjects, the sponsor will determine the final planned sample size in the discussion with the statistical advisor.

Null and alternative hypotheses in statistical tests are as follows:

- Null hypothesis H_0 : $\lambda_T/\lambda_C = 1$
- Alternative hypothesis H_1 : $\lambda_T/\lambda_C \neq 1$
- λ_C : Hazard with S-1/CDDP
- λ_T : Hazard with TAS-118/L-OHP

A list of powers provided when expected MST is changed in each arm is shown in Table 2-1.

Table 2-1 Changes in power (%) in the final analysis when expected MST is changed

MST (months) in TAS-118/L-OHP arm	MST (months) in S-1/CDDP arm						
	12	13	14	14.5	15	16	17
17	95.3	79.8	52.4	38	25.4	9.1	2.4
18	98.8	92.4	74.5	61.5	47.5	23	8.5
19	99.8	97.7	88.9	80.4	69.2	43.2	21
19.33	99.9	98.5	92	85	75.2	50.3	26.6
20	100	99.4	96.1	91.8	85	64.2	39.4
21	100	99.9	98.8	97.1	93.9	80.9	59.5
22	100	100	99.7	99.2	97.9	91.3	76.6

The powers were calculated with a total number of events of 437 and a two-sided significance level of 4.899%.

The power selected in this study is underlined.

The overall power (a probability that the test is significant under the alternative hypothesis either in the interim analysis or the primary evaluation) is 85.1% in this study, including the interim analysis. This power was calculated using logarithmic transformation and normal approximation of the expected hazard ratio according to the following formulas:

$$\text{Total power} = 1 - \Pr\left(Z_1 > z_{\frac{\alpha_1}{2}}, Z_2 > z_{\frac{\alpha_2}{2}}\right)$$

$$\begin{pmatrix} Z_1 \\ Z_2 \end{pmatrix} \sim N\left(\begin{pmatrix} \log(\Lambda) \times \sqrt{\frac{N_1}{4}} \\ \log(\Lambda) \times \sqrt{\frac{N_2}{4}} \end{pmatrix}, \begin{pmatrix} 1 & \sqrt{\frac{N_1}{N_2}} \\ \sqrt{\frac{N_1}{N_2}} & 1 \end{pmatrix}\right),$$

α_1 : two-sided significance level in an interim analysis,

α_2 : two-sided significance level in the primary analysis for the primary evaluation,

N_1 : required number of events in an interim analysis, N_2 : required number of events in the final analysis

2.1.3. Change in the Required Number of Events in the Analysis for Primary Evaluation

Ramucirumab was approved in Japan in March 2015 and Korea in April 2015. As of March 2017, when the independent data monitoring committee (IDMC) emergency meeting was held, an application was filed for the approval of partial changes to marketing approval matters on the indication of nivolumab for gastric cancer in Japan in December 2016, and early use of nivolumab was expected.

Using these drugs, which were not considered at the time of study initiation, in subsequent therapy may prolong OS and reduce the power assumed before study initiation. The IDMC was therefore consulted for that concern in the IDMC emergency meeting in March 2017 and recommended that the required total number of events be changed to 491 events. Accordingly, the protocol was revised on April 12, 2017, to change the required number of events to 491 in the analysis for the primary evaluation.

2.2. Subject Registration and Randomization Method

2.2.1. Randomization Method

Subjects will be randomized in a 1:1 ratio to TAS-118/L-OHP (study arm, Arm A) or S-1/CDDP (control arm, Arm B).

Treatment assignment will be performed *via* an interactive web response system (IWRS) using a dynamic allocation method (minimization method) stratified by the following allocation adjustment factors:

- Measurable lesion: (yes, no)
- Eastern Cooperative Oncology Group (ECOG) performance status (PS): (0, 1)
- Country: (Japan, Korea)

3. Data to Be Used in Statistical Analysis and Analysis Populations

3.1. Materials and Data Other Than Case Report Forms

A list of materials and data required for statistical analysis other than the case report form (CRF) is presented in Table 3-1.

Table 3-1 Materials and data required for statistical analysis other than the CRF

Parameters	Materials or data	Remarks
Randomization	True allocation key	To identify the treatment randomized to each subject.
Data at randomization	Patient baseline characteristics information, such as the allocation adjustment factors used for patient randomization, that is provided with the true allocation key by the trial registration office	To summarize the information using both data at randomization and CRF data.
Coding to MedDRA terms	Corresponding table between terms of adverse events, medical history, and complications recorded by the investigator and MedDRA terms	To summarize the proportion of subjects with adverse events by using unified terms.
Name of concomitant medications and therapies	Corresponding data between terms of concomitant medications recorded by the investigator and WHO Drug Dictionary	To summarize concomitant medications by using unified terms.
Inclusion of subjects	Flag of the inclusion of each subject in each analysis population	To identify which analysis population each subject is included in.
Significance level in the primary analysis for the primary evaluation	Significance level calculated and information in interim analyses	To calculate the significance level in the primary analysis.
Information on follow-up censoring	Date of follow-up censoring	To reflect the date of follow-up censoring as the date of censoring in survival analysis in subjects whose consent to survival information follow-up cannot be confirmed.
Information on deviations	Nature of deviation and important deviation flag	To provide a list of deviated subjects.
Institutional normal range	Institutional normal range of laboratory values	To determine whether laboratory values are normal or abnormal or evaluate the change in CTCAE grade.

3.2. Analysis Populations

A list of the name and definition of analysis populations is presented in Table 3-2.

If there are any problems with the inclusion of subjects in each analysis population except the criteria listed below, the sponsor will determine in which population the subject should be included before analysis in the discussion with the medical advisor.

Table 3-2 Definitions of analysis populations

Analysis populations	Definition
Enrolled population	All patients enrolled in this trial
As-treated (AT) population	Enrolled patients who received at least one dose of the study drug
Full analysis set (FAS)	Patients in AT population who have advanced gastric cancer at randomization
Tumor response-evaluable population	Patients in FAS population who have measurable lesions (at least one target lesion) at baseline and are evaluated for tumor responses at least once during treatment with the study drug

4. Timing of Analyses and Significance Level

In this study, two interim analyses were planned and implemented before the analysis for the primary evaluation. Based on the results of the two interim analyses and IDMC reviews, the timing of the analysis for the primary evaluation is defined in Table 4-1.

In the analysis for the primary evaluation, whether TAS-118/L-OHP is superior to S-1/CDDP with respect to OS will be tested in the FAS population. As the test method, a stratified log-rank test will be conducted according to the following allocation adjustment factors: measurable lesion (yes, no), ECOG PS (0, 1), and country (Japan, Korea).

Table 4-1 Timing of each analysis and significance level

	Timing of analysis	Significance level at sample size determination
First interim analysis	When the number of death events reaches 100 (Date: April 22, 2016)	Not tested
Second interim analysis	When the number of death events reaches 219 (Date: November 30, 2016)	0.305%
Analysis for the primary evaluation	When the required number of death events, 491, is confirmed	4.899%

These significance levels were calculated using the Lan and DeMets method (O'Brien-Fleming type) at the time of sample size determination. The significance levels to be spent will be recalculated in the interim analyses and the analysis for the primary evaluation. The procedures for recalculation are presented in Section "5.2.4.12 Log-Rank Test Using Recalculated α "

5. Endpoints and Common Considerations for Statistical Analysis

5.1. Endpoints

The definition of efficacy, safety, and compliance is presented below.

Based on the data cutoff date decision record created according to the data cutoff procedures, the range of entry data will be identified. In the primary analysis, the cutoff date is handled as the event date in the 491st subject.

5.1.1. Efficacy Endpoints

The efficacy endpoints in this study are the primary endpoint of OS and the secondary endpoints of PFS, TTF, ORR, and DCR, as well as the duration of overall response, the duration of complete response, and tumor shrinkage rate.

5.1.1.1 OS

Overall survival is defined as the time (in months) from the date of randomization to the date of death due to any cause. In the primary analysis, subjects who are not known to be dead or are alive as of the cutoff date will be censored at the date of the last survival confirmation or the cutoff date, whichever comes first.

The OS cutoff date used for the analysis is defined as the event date in the 491st subject in the FAS population. In the analyses in the enrolled population, the cutoff date is defined as the event date in the 491st subject in the enrolled population.

A list of the definition of OS events is presented in Table 5-1.

Table 5-1 Definition of OS events

	Case	Date
Event	Subjects died before the cutoff date.	Date of death
Censoring	Subjects failed to be followed up for death or are alive as of the cutoff date.	Date of the last survival confirmation* ¹ or the cutoff date, whichever comes first

*1: The latest date among the dates recorded in all pages of the CRF

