6.2. Sensitivity Analyses of Primary Analysis

- In the FAS population, a stratified log-rank test will be conducted according to the allocation adjustment factors entered in the CRF.
- Using a log-rank test without any allocation adjustment factors, the analysis will be conducted.
- In the enrolled population, the primary analysis will be conducted.

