6.3. Secondary Analyses of Primary Endpoint

- With the date of observed death as the event date and the date of the last survival confirmation as the censoring date, without consideration of the cutoff date, the same analysis as the primary analysis will be conducted.

The following secondary analyses of the primary endpoint will be conducted in the FAS population:

- The survival curve, MST, and 95% confidence interval will be estimated in each treatment arm. The between-group difference in MST and its 95% confidence interval (by the bootstrap method) will also be calculated. The RMSTs and their 95% confidence intervals will be estimated, with an RMST boundary of 3 years (36 months). In addition, the between-group difference in RMST and its 95% confidence interval will be calculated.
- The number of subjects at risk at 3-month intervals, cumulative event-free rate, and median follow-up period (time to censoring) and its 95% confidence interval will also be presented.
- Using a Cox proportional hazards model with the allocation adjustment factors of study treatment (1: TAS-118/L-OHP, 0: S-1/CDDP), ECOG PS (0, 1) at randomization, measurable lesion (1: yes, 0: no) at randomization, and country (1: Japan, 0: Korea) as covariates and a stratified Cox proportional hazards model according to the allocation adjustment factors, the hazard ratio for each covariate and its confidence interval will be estimated. To estimate the confidence interval of the hazard ratio corresponding to the primary analysis, the confidence level of the stratified Cox proportional hazards model is defined as follows: 100–significance level (%) used for the primary analysis. The 95% confidence interval will also be estimated.
- Using a Cox proportional hazards model with the allocation adjustment factors of study treatment (1: TAS-118/L-OHP, 0: S-1/CDDP), ECOG PS (0, 1) entered in the CRF, measurable lesion (1: yes, 0: no) entered in the CRF, and country (1: Japan, 0: Korea) as covariates and a stratified Cox proportional hazards model according to the allocation adjustment factors, the hazard ratio for each covariate and its 95% confidence interval will be estimated.
- Using a Cox proportional hazards model with study treatment (1: TAS-118/L-OHP, 0: S-1/CDDP) as a covariate, the hazard ratio for the covariate and its 95% confidence interval will also be estimated.

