7.1.2. PFS

- Progression-free survival will be analyzed in the same manner as specified in Section “6. Primary Endpoint Analyses” (excluding the analyses of RMST and between-group difference in MST). In

the analyses using the allocation adjustment factors, only data entered in the CRF will be used with a confidence level of 95% for all confidence intervals.

- In the enrolled population, the same analyses will be conducted.

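### The enrolled-population OS sensitivity analysis has its own, usually earlier, cutoff, so it changes follow-up as well as population

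*SAP*

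**What the plan says.** SAP 5.1.1.1 sets two OS cutoffs. For the primary analysis: "The OS cutoff date used for the analysis is defined as the event date in the 491st subject in the FAS population". For the other population: "In the analyses in the enrolled population, the cutoff date is defined as the event date in the 491st subject in the enrolled population". Under the primary-analysis rule, a patient not known to have died by the cutoff "will be censored at the date of the last survival confirmation or the cutoff date, whichever comes first". Table 5-1 gives the same rule without limiting it to one population.

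SAP 6.2 lists the enrolled run among the sensitivity analyses of the primary analysis: "In the enrolled population, the primary analysis will be conducted". SAP 6.3 adds a run on OS in which, "without consideration of the cutoff date, the same analysis as the primary analysis will be conducted".

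SAP 3.2 (Table 3-2) nests the populations. The FAS is the treated patients with advanced gastric cancer at randomization, and the treated patients are a subset of those enrolled. The planned sizes are in SAP 2.1.1: "Target number of patients at study initiation: 686 subjects" and "target number of patients included in the FAS: 650 subjects".

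**The concern.** The enrolled-population run restores the randomized patients whom the FAS leaves out: those never dosed and those without advanced gastric cancer. In an open-label trial that is a useful check, because the decision not to start treatment can depend on the assigned arm. The check reads cleanly only if the population is the one thing that changes.

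As written, the cutoff changes too. Deaths outside the FAS count toward the 491, so the enrolled cutoff arrives sooner, and FAS patients who die between the two dates move from event to censored. If the two results differ, the reader cannot tell how much comes from the restored patients and how much from the shorter follow-up. If they agree, two offsetting changes cannot be ruled out. What is at stake is the interpretation of a robustness check. The primary test and its type I error are not affected.

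**Working it through.** **1. The plan's own figures.** Inputs from SAP 2.1.2: hazard ratio 0.75, two-sided level 4.899% (z = 1.9687), power 85% (z = 1.0364), 1:1 allocation.

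- Events = (1.9687 + 1.0364)² / (0.25 × (ln 0.75)²) = 9.031 / 0.02069 = 436.5, so 437 as stated.
- Medians of 14.5 and 19.33 months give hazards ln 2/14.5 = 0.04780 and ln 2/19.33 = 0.03586 per month. The SAP's formula for the probability of death, with accrual X = 17 and follow-up Y = 19 months, gives 0.7240 (control) and 0.6212 (experimental), mean 0.6726.
- FAS size = 437/0.6726 = 649.7, so 650 as stated.
- Per arm, 325/0.95 = 342.1, rounded up to 343, hence 686 enrolled as stated.

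**2. Direction of the difference.** Every FAS death is also an enrolled death, so on any date enrolled deaths are at least as many as FAS deaths. The enrolled count cannot reach 491 later than the FAS count, and it reaches 491 earlier if any non-FAS patient has died by then (ties aside). This needs no model.

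**3. Number of FAS deaths censored.** Ignoring ties, the enrolled analysis holds 491 deaths. If k of them are non-FAS, then 491 − k are FAS deaths and k FAS deaths from the primary analysis drop out. With equal mortality and complete capture, k = 491 × (non-FAS patients)/686.

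**4. Distance between the cutoffs.** Using the same exponential model, solve N × P(death by Y) = 491 for Y, once with N = FAS size and once with N = 686. Accrual of 17 or 19 months gives the same gaps to the precision shown. The months below use 19, counted from the start of accrual.

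| FAS size (of 686) | FAS cutoff | Enrolled cutoff | Gap (months) | FAS deaths censored | Enrolled deaths at FAS cutoff |
|---|---|---|---|---|---|
| 650 (planned) | 44.3 | 40.6 | 3.7 | 491 × 36/686 = 25.8 | 518 |
| 652 (5% excluded) | 44.0 | 40.6 | 3.5 | 491 × 34/686 = 24.3 | 517 |
| 672 (2% excluded) | 41.9 | 40.6 | 1.3 | 491 × 14/686 = 10.0 | 501 |
| 679 (1% excluded) | 41.2 | 40.6 | 0.6 | 491 × 7/686 = 5.0 | 496 |

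**5. Incomplete capture of deaths.** Protocol 11.8 requires survival follow-up of treated patients, and non-FAS patients include the untreated. With 650 FAS and 36 non-FAS patients, if only half of the non-FAS deaths are captured, about 13 FAS deaths are censored and the gap is about 2.0 months. If none are captured, both are zero. The ceiling at planned numbers is 36, reached only if all 36 non-FAS patients die before the enrolled cutoff.

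**6. Precision.** With SE(log HR) ≈ 2/√events:

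- 491 events: 0.0903, power at HR 0.75 of 0.889
- 518 events: 0.0879, power 0.904

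The primary and the 491-event enrolled run have the same nominal precision. The common cutoff adds a little to the enrolled run.

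**7. Likely shift from the cutoff alone.** Under proportional hazards, an earlier calendar cutoff does not move the expected log HR. The chance shift between 467 and 491 FAS events has SD ≈ √(4/467 − 4/491) = 0.020, or about 2% in the hazard ratio.

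**The case against.** The strongest defence is that the design is event-driven. Fixing 491 events in each population holds statistical information constant, and the two analyses then have the same nominal power. That is a coherent aim, but nothing requires it in an analysis that carries no alpha, and the 491-event run can be kept next to a common-date run.

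The second defence is size. The censoring applies to both arms by calendar date, the precision cost is under 3%, and step 7 puts the chance shift near 2%. All of this stands, and it limits the weight of the point. It does not restore a comparison that changes one thing only.

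The third is that SAP 6.3 already plans a run without a cutoff. That run repeats the primary analysis, so by its wording it is in the FAS. It also lengthens follow-up, so it does not reproduce the earlier enrolled date. It shows whether the FAS result depends on the cutoff but does not supply an enrolled analysis at the FAS date.

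A reader might also infer four stronger claims that the documents do not support:

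- **Known deaths are recoded as alive.** They are administratively censored at a date set by rule, which is neither misclassification nor a bias in itself.
- **A fixed number of about 25 deaths is lost.** The documents give no actual non-FAS count and no non-FAS deaths, so the figure depends on assumptions.
- **No information is missing.** Follow-up of untreated patients is not clearly required, and SAP Table 3-1 foresees patients whose consent to survival follow-up cannot be confirmed.
- **This is the only planned analysis of all randomized patients.** For PFS, SAP 7.1.2 says "In the enrolled population, the same analyses will be conducted", and SAP section 9 refers the full list of analyses to a separate output plan. Whether the OS cutoff sentence governs that PFS analysis is not stated.

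**Conclusion.** The point holds for OS. The enrolled-population sensitivity analysis differs from the primary analysis in both population and cutoff whenever a non-FAS patient has died by the enrolled cutoff, and neither document describes an enrolled OS run at the FAS cutoff.

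The size depends on 686 enrolled, equal mortality inside and outside the FAS, full capture of deaths, and exponential survival for the gap in months. With about 5% excluded, the gap is 3.5 to 3.7 months and 24 to 26 FAS deaths are censored. With 2% excluded it is about 1.3 months and 10 deaths. The possible range at planned numbers is 0 to 36, with lower values if deaths in untreated patients are incompletely captured.

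The cost is comparability, plus up to about 27 available enrolled deaths left unused (518 − 491). It is not bias, and the loss of precision is small: SE of log HR 0.090 against 0.088. This is a cheap improvement; the validity of the primary analysis is not in question.

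**What to change.** In SAP 5.1.1.1, state that the enrolled-population OS sensitivity analysis uses the same calendar cutoff date as the FAS primary analysis. It then contains every FAS event plus the captured deaths among non-FAS patients by that date, and a difference from the primary result reflects the restored patients alone. The 491-event enrolled cutoff can stay as a supplementary run if equal information is wanted.

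Limit the change to OS. PFS and TTF refer to a data cutoff that the OS sentence has not been shown to govern.

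The cost is one changed sentence or one extra run, with no new data. The enrolled analysis will have more than 491 events if any non-FAS deaths are captured. This is harmless, because the formal test is in the FAS and this analysis spends no alpha.
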